We are postulating that by application of CGMS for 2 weeks glycemic patterns of individual patients will be identified and the education provided in this regard will change the insight of the individual towards his disease which will culminate in better longer term blood glucose control and already previous studies have shown that glucose readings from the most recent 14 days correlate strongly with 3 months of mean blood glucose, time in ranges, and hyperglycemia metrics (33,34).

Primary objective:

To study the effects of rtCGM vs isCGM on:

- Reduction in HbA1c (at the end of 3 months).

Secondary objectives:

- Reduction in glycemic variability.
- Reduction in hypoglycemic events in adults with Type-1 Diabetes.
- Reduction in Fructosamine (at the end of 2 weeks).
- Quality of life as assessed by QOLID (Nagpal etal) Questionnaire

MATERIALS AND METHODS

1. **Study design:** Open label crossover RCT with 3 arms
2. **Sample size:** Sample size of 17 is requires for a power of 80% to detect 0.5% change in HbA1c between both groups with an alpha of 0.05, Assuming 10% attrition in each group 20 patients will be recruited in all rt-CGMS and is-CGMS and 40 in SMBG arms.
3. **Subjects:** Patients attending Endocrinology OPD at PGIMER Chandigarh
4. **Study Period:** 15th June 2023 to 15th February 2024(last enrolment on 15th August 2023) and last follow up on 15th February 2024.
5. **Study Center:** PGIMER, Chandigarh
6. **Study Population:** Patients who fulfill inclusion and exclusion criteria will be recruited from OPD.

Inclusion criteria :

- Adolescents and adults ≥ 15 years with Type-1 Diabetes mellitus defined by any of the following;
 - Diabetic Ketoacidosis or ketonemia or ketonuria at diagnosis with insulin dependence for survival since diagnosis OR
 - Insulin dependence for survival since diagnosis and any one of the following autoantibody positivity: GAD-65 or IA-2
- Patients on Basal bolus regimen (**Glargine as basal and lispro/Aspart/Glulisine as bolus**);
- Duration of Diabetes > 2 years;

- Insulin dose requirement of at least 0.5U/kg
- HbA1c 8%-12%;
- Gold score<4;
- No previous experience with rt-CGMS and/or is-CGMS;
- Euthyroid status;
- If hypothyroid, then on stable dose of Levothyroxine for last 3 months with normal T4 level;
- Urine albumin creatinine ratio<300 mg/g of Creatinine;
- Those willing to give informed consent prior to enrolment.

EXCLUSION CRITERIA:

- LADA or Secondary Diabetes
- eGFR<60ml/min/1.73 m^2
- Celiac disease;

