- Hb<12g/dl for males and <11g/dl for females;
- Hypoglycemia unawareness defined by Gold score \geq 4;
- HbA1c>12%;
- DKA in previous 3 months;
- Severe Non proliferative Diabetic retinopathy/Proliferative DR/Macular edema;
- Pregnancy;
- Lactation;
- Willing to become pregnant during study;
- Requiring MRI for any existing condition;
- Any chronic illness.

METHODOLOGY

Participants meeting inclusion criteria will be randomized to rt-CGMS, is-CGMS and SMBG arms. Randomization will be done using computer generated random number list. Blocks of patients with HbA1c 8%-10% and 10%-12% will be distributed equally in all 3 groups.

Sample Size: With a 1:1:2 randomization ratio in 3 arms with sample size of 20:20:40 participants in each groups will be required.

Initial training of 2 weeks for all enrolled patients in each of 3 groups about the disease itself, ICR, ISF, carbohydrate counting and bolus dose adjustment based on these parameters will be done, for premeal boluses. **Only those patients will be enrolled who are using Lispro/Aspart/Glulisine for their diabetes control.** All adults enrolled in the rt-CGM group will be placed on rt-CGM Medtronic CGMS for 2 weeks and finger-prick blood glucose will also be monitored by glucometer (SMBG) 3 times on day 1 and then at least 2 times per day with proper record of time. All patients will use same glucometer for SMBG. Physical exercise of at least 30 mins aerobic activity will be required in all patients.

After a week a new Medtronic CGMS will be applied as per the manufacturer recommendation. Those randomized into is-CGM will be placed on Abbott Libre Flash system for 2 weeks. A 3rd group on SMBG will also be there (doing SMBG 4 times a

day- Before breakfast, Before Lunch, and Before Dinner and post meal (after any one meal on rotational basis) and **7 point profile once a week on Sunday**).

During this 2 week intervention phase all the patients will be monitored daily telephonically along with once in a week follow-up visit.

Fructosamine assay will be repeated after 2 weeks in rt-CGMS and is-CGMS groups and glycemic control compared. Thereafter the 3 groups shall use SMBG for monitoring glycemic status as in SMBG group and HbA1c will be repeated at the end of 3 months.

CGMS metrics of the 2 weeks (TBR, TIR ,TAR etc) will be compared in both groups as per ADA recommendations and those with <70% data available will be kept on a new device.

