At the end of 3 months direct cross-over of rt-CGMS group to new is-CGMS group and is-CGMS group to new rt-CGMS group will be done and again fructosamine assay shall

be done at the baseline and at the end of 2 weeks. Thereafter, all the 3 groups shall use same glucometer for SMBG till the end of 6 months where HbA1c will be estimated.

[figure not shown]
Hence, for each participant total 6 months of data will be recorded. Individuals will act as their own control thereby removing confounding factors in analysis

[figure not shown]
be done at the baseline and at the end of 2 weeks. Thereafter, all the 3 groups shall use same glucometer for SMBG till the end of 6 months where HbA1c will be estimated.

[figure not shown]
Hence, for each participant total 6 months of data will be recorded. Individuals will act as their own control thereby removing confounding factors in analysis.

[figure not shown]
All these insulins and CGM systems are a part of routine standard care in management of Type-1 Diabetes Mellitus as endorsed by American Diabetic Association in 2022.

FLOW CHART OF STUDY PROTOCOL

OUTCOME VARIABLES TO BE STUDIED

- Glycemic variability as assessed by CGMS
- Daily average insulin requirement per kg body weight
- Fructosamine assay after 2 weeks in rt-CGMS group and is-CGMS group and HbA1c in each of the 3 groups at end of 3 and 6 months respectively;
- Number of hypoglycemic events especially nocturnal and exercise related events;
- Any complications related to CGM;
- Quality of Life by QOLID (Nagpal et al) Questionnaire.

Statistical Analysis:

Statistical analysis will be performed according to the results obtained from parameters. Discrete categorical data will be represented in the form of either a number or a percentage (%), continuous data, assumed to be normally distributed, will be written as either in the form of its mean and standard deviation or in the form of its median and interquartile range, as per the requirement. The normality of quantitative data will be checked by measures of Kolmogorov-Smirnov tests of normality. ANOVA or Mann Whitney U test will be applied to compare 3 groups at a time depending upon the normality of the data. Proportions will be compared using Chi square or Fisher's exact test, depending on their applicability for 3 groups. All the statistical tests will be two-sided and will be performed at a significance level of $P < 0.05$. Analysis will be conducted using IBM SPSS STATISTICS (version 22.0)

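### Hypoglycaemic events are planned as a raw number with no denominator; if they are counted from sensors, the rt-CGM v is-CGM comparison depends partly on how each device records

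*Combined protocol and SAP*

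**What the plan says.** The secondary objectives include "Reduction in hypoglycemic events in adults with Type-1 Diabetes". Under the outcome variables this becomes "Number of hypoglycemic events especially nocturnal and exercise related events". No glucose threshold, minimum duration, data source, counting window or per-time denominator is given.

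The Statistical Analysis section assigns no test to this outcome by name. For quantitative data it offers only: "ANOVA or Mann Whitney U test will be applied to compare 3 groups at a time depending upon the normality of the data". It contains no rate, offset, count model or paired method.

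The table of device differences in the introduction gives one reading every 15 minutes for the is-CGM device and every 5 minutes for the rt-CGM device. Each is worn for two weeks per period, for example "Those randomized into is-CGM will be placed on Abbott Libre Flash system for 2 weeks".

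On incomplete data, the Methodology says only that "those with <70% data available will be kept on a new device". It says nothing about adjusting for observed time. The same sentence refers to ADA recommendations for sensor metrics and lists the time-in-range family. Event counts are not named there.

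**The concern.** A raw count is comparable between devices only if both have the same chance of registering an episode and are observed for the same time. Neither is secured here. The 5-minute device takes three readings for each one on the 15-minute device. Coverage may also differ: the introduction describes rt-CGM as transmitting automatically and is-CGM as needing the user to scan, and the plan does not correct for missing hours.

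The usual protection of a crossover is lost on this point. Each patient is their own control for glucose behaviour, but recording switches whenever the device switches, so a recording artefact is fully confounded with the device effect. A secondary objective could then appear to favour one device when true event rates are equal.

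**Working it through.** The plan gives no expected event rate, spread or power for this outcome, so there is no planned figure to reproduce. The checks below size the two mechanisms, taking events to come from sensor data.

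**1. Readings available.** Fourteen days is 14 × 1,440 = 20,160 minutes. At full capture this gives 20,160/5 = 4,032 readings for rt-CGM and 20,160/15 = 1,344 for is-CGM.

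**2. Recording interval.** Assume episode lengths are exponential with mean m minutes (m is not in the documents). The chance that at least one reading at interval T falls inside an episode is (m/T)(1 − exp(−T/m)). Requiring a run of readings that spans s minutes multiplies this by exp(−s/m).

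For m = 30, the 5-minute device gives (30/5)(1 − exp(−5/30)) = 0.921 and the 15-minute device (30/15)(1 − exp(−15/30)) = 0.787. The ratio is 0.921/0.787 = 1.17.

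| Event rule (5-min device v 15-min device) | m = 15 | m = 30 | m = 60 |
|---|---|---|---|
| one low reading v one | 1.35 | 1.17 | 1.08 |
| four v two (both span 15 min) | 1.35 | 1.17 | 1.08 |
| three v two (10 v 15 min) | 1.88 | 1.38 | 1.18 |
| three v one (10 v 0 min) | 0.69 | 0.84 | 0.92 |

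The largest and the reversed ratios come from rules that ask different durations of the two devices.

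**3. Sensor noise.** Glucose traces were simulated for 300 patients over 14 days (all settings assumed: log-normal, mean 160 to 200 mg/dL, CV 36 to 38%, smooth correlation over 40 to 240 minutes). Each trace was read at 5 minutes and at every third reading. Counting every run below 70 mg/dL gives about 1.05 to 1.20 times as many events at 5 minutes without noise, and 1.43 to 1.87 with 3% independent noise per reading. The excess is mostly flicker across the threshold. Rules with matched 15-minute spans give about 1.03 to 1.20. Time below range is unchanged by the recording interval.

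**4. Coverage.** At equal true rates the count ratio equals the coverage ratio. As an illustration with assumed values, 75% v 95% gives 0.75/0.95 = 0.79. At exactly 70% of 14 days, 9.8 days are observed, and full capture gives 1/0.70 = 1.43 times the count. Warm-up alone is trivial: two rt-CGM sensors at under 2 hours each and one is-CGM sensor at 1 hour leave at least 332 v 335 of 336 hours, a ratio of 0.99.

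**5. Effect on the test.** The documents give "with an alpha of 0.05" and "All the statistical tests will be two-sided". The event rate and spread come from the trial in impaired awareness or severe hypoglycaemia described in the literature review: mean 10.8, SD 10.0 per 28 days, taken as 5.4 per 14 days. The dispersion is k = 10.8²/(10.0² − 10.8) = 116.64/89.2 = 1.31. True rates are set equal and all capture loss is placed on one device (3,000 runs per case).

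| Relative capture | 20 per arm, raw counts (Mann-Whitney / t) | 40 paired, raw counts (paired t) | 40 paired, rates |
|---|---|---|---|
| 0.85 | 7% / 8% | 33% | about 5% |
| 0.70 | 16% / 17% | 89% | about 5% |

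The paired case assumes that all 40 CGM patients complete both periods. Pairing increases the false-positive rate because it removes between-patient variation and leaves the artefact.

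**6. The SMBG arm.** Four checks a day, treated as evenly spaced (T = 360), would meet about 4%, 8% or 17% of episodes of mean 15, 30 or 60 minutes. Sensor counts and fingerstick counts therefore cannot share one three-group test.

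**The case against.** The strongest objection is that the plan never says events come from sensors. It marks glycaemic variability as CGMS-based but does not mark events that way. Fingersticks, daily telephone contact and patient report are all available, the SMBG arm has no sensor, and exercise-related events need information beyond the trace. This stands as a condition on the whole point. If events are reported or fingerstick-based, the 5 v 15 minute argument falls away. A denominator is still needed, because the rt-CGM arm does at least two checks a day and the SMBG arm four.

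Three stronger readings are tempting and are not supported:

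- A reader might take 70% as the lowest coverage admitted to analysis. The text sets a trigger for a new device. It sets no floor, so observed time could be lower, or longer if a replacement adds days. The documents give no coverage figures by device, and random loss that is equal across devices adds noise, not bias.
- A reader might infer that less frequent recording always yields fewer events. The three v one row shows the reverse; direction depends on the missing event rule.
- A reader might expect close to a doubling. That needs single-reading counting with assumed noise, or mismatched durations with short episodes.

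It is also fair that the false-positive table puts all the loss on one arm, that independent-group error at 0.85 is only 7% to 8%, and that the rate and spread come from a population with impaired awareness, which this trial excludes. Negative binomial modelling is one option: dividing by captured time already restores about 5%.

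**Conclusion.** The point holds in conditional form. A raw number with no denominator, tested by ANOVA or Mann-Whitney, is a weaker method than a rate on a common grid. If events are sensor-derived, the rt-CGM v is-CGM count partly reflects the device's recording.

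Under one common duration rule the recording effect is small to modest, roughly 1.0 to 1.4. It is larger if single noisy readings count and below 1 under a three v one rule. Coverage differences pass straight through to the count, but how large they will be is unknown. The mechanism rests on the plan's own recording intervals. The sizes rest on assumed episode lengths, noise and coverage.

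This is minor to moderate: a secondary, unpowered outcome, with time below range also compared and unaffected by the recording interval.

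**What to change.** - State the data source and counting window for hypoglycaemic events.
- For sensor events, keep every third reading of the 5-minute stream so that both devices sit on a 15-minute grid. Apply one identical rule, with the same threshold and minimum duration, to both.
- Compare events per valid sensor hour within patient, with device and period terms. A negative binomial model with log valid hours as offset and patient as cluster would do this; a paired comparison of rates is an acceptable alternative. Report the rate ratio with its 95% CI.
- For nocturnal events, use valid night hours as the denominator.
- Report SMBG-detected or patient-reported events separately, and do not pool them with sensor-counted events in the three-group test.

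The cost is a few sentences in the analysis section and one data-processing step, with no new data. The downside is that some very short episodes, visible only at 5 minutes, will not be counted.

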Beck et al conducted a Randomized clinical trial conducted between October 2014 and May 2016 at 24 endocrinology practices in the United States that included 158 adults with type 1 diabetes who were using multiple daily insulin injections and had hemoglobin A1c (HbA1c) levels of 7.5% to 9.9%. Random assignment 2:1 to CGM ($n = 105$) or usual care (control group; $n = 53$) was done in this study and the difference in change in central-laboratory-measured HbA1c level was compared from baseline to 24 weeks. Also, secondary outcome as duration of hypoglycemia at less than 70mg/dL, measured with CGM for 7 days at 12 and 24 weeks was reported. It was found that mean HbA1c reduction from baseline was 1.1% at 12 weeks and 1.0% at 24 weeks in the CGM group and 0.5% and 0.4%, respectively, in the control group (repeated-measures model $P < .001$). At 24 weeks, the adjusted treatment-group difference in mean change in HbA1c level from baseline was $-0.6%$ (95% CI, $-0.8%$ to $-0.3%$; $P < .001$) and median duration of hypoglycemia at less than <70 mg/dL was 43 min/d (IQR, 27-69) in the CGM group vs 80 min/d (IQR, 36-111) in the control group ($P = .002$). Severe hypoglycemia events occurred in 2 participants in each group. This trial

revealed that among adults with type 1 diabetes who used multiple daily insulin injections, the use of CGM compared with usual care resulted in a greater decrease in HbA1c level during 24 weeks.

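### DKA is not an outcome in any arm and severe hypoglycaemia is not separated out; beyond an undefined count of hypoglycaemic events, the only harm item is tied to the CGM device

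*Combined protocol and SAP*

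**What the plan says.** Two entries under Outcome Variables to be Studied concern harm. One is "Number of hypoglycemic events especially nocturnal and exercise related events"; it matches the secondary objective "Reduction in hypoglycemic events in adults with Type-1 Diabetes". Neither is restricted to an arm or to sensor wear, and neither gives a glucose threshold, severity grade, time window or method of ascertainment. The other entry is "Any complications related to CGM".

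Among the trial's own rules, DKA appears only in eligibility: at diagnosis in the Inclusion criteria, and as "DKA in previous 3 months" in the Exclusion Criteria.

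On contact, Methodology says: "During this 2 week intervention phase all the patients will be monitored daily telephonically along with once in a week follow-up visit". The crossover paragraph does not repeat this for the second wear fortnight. Methodology also describes "Initial training of 2 weeks for all enrolled patients in each of 3 groups", which includes "carbohydrate counting and bolus dose adjustment based on these parameters will be done, for premeal boluses". After each wear phase all groups monitor by SMBG, with HbA1c at months 3 and 6. No event collection is described for the training weeks or the SMBG months. The flow chart is not shown in the text available.

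**The concern.** The Hypothesis section postulates that a two-week wear plus education changes behaviour and so improves control over the longer term. The primary endpoint is HbA1c at 3 months. Tighter control after insulin adjustment can bring hypoglycaemia, and DKA is the opposite failure. The protocol itself treats both as important: its introduction cites fewer admissions for severe hypoglycaemia and/or DKA as a benefit of flash CGM, and its Review of Literature reports fewer such admissions in a 24-month cohort.

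A harm outcome that requires attribution to the sensor cannot record a DKA episode or a severe low caused by dosing. It is empty in the SMBG arm by construction. The hypoglycaemia count merges mild and severe events. If serious events are not asked about as they occur, the analyst cannot reliably reconstruct them afterwards, and an HbA1c gain would be reported without the safety information needed to read it.

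**Working it through.** The plan gives no safety figure to reproduce. The check has three parts.

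**1. What each outcome can capture, as written**

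| Event | Hypoglycaemia count | CGM-complication item |
|---|---|---|
| Severe hypoglycaemia, CGM arms | Yes, but not separated from mild events | Only if attributed to the device |
| Severe hypoglycaemia, SMBG arm | Yes, but not separated from mild events | No |
| DKA, CGM arms | No | Only if attributed to the device |
| DKA, SMBG arm | No | No |
| Other diabetes-related admission, SMBG arm | No | No |

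Training is given to patients already in their three groups, so events in those weeks come after randomisation and belong in the comparison.

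**2. Stated contact as a share of follow-up**

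- Input: 2 weeks of calls and visits (Methodology); 3 months is about 13 weeks, 6 months about 26.
- Primary HbA1c period: 2/13 = 15%.
- Six months, contact in the first fortnight only: 2/26 = 8%.
- Six months, contact repeated after crossover: 4/26 = 15%.
- SMBG stretch after wear: 13 − 2 = 11 weeks if the 3 months start at wear, or 13 − 2 − 2 = 9 weeks if they include training. The text does not say which.

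These are shares of time under stated contact. They are not shares of events recorded.

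**3. How many severe hypoglycaemia cases to expect**

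Inputs come from the Review of Literature:

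- The 24-week US trial of CGM against usual care, 158 adults: "Severe hypoglycemia events occurred in 2 participants in each group", so 4 patients. Rate 4/158 = 2.53% per 24 weeks. Scaled: 4/158 × 26/24 × 80 = 2.2 patients.
- The Swedish crossover trial, two 26-week periods, 142 patients with data in both: 5 patients on conventional treatment and 1 on CGM, so 6. Rate 6/(2 × 142) = 2.1% per 26 weeks. Scaled: 6/284 × 80 = 1.7 patients.

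For a device arm of 20, a quarter of these totals: 1.7/4 = 0.4 to 2.2/4 = 0.6 patients over 26 weeks. The documents give no DKA rate, so no DKA count is projected.

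**The case against.** The strongest reply is that the plan does address hypoglycaemia, the main expected harm: it is a secondary objective and a listed outcome, unrestricted by arm. The protocol also says 6 months of data will be recorded for each participant and keeps all groups on SMBG throughout. This stands, and it rules out several stronger readings.

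- A reader might infer that harm collection is confined to device complications. The hypoglycaemia entries show that it is not.
- A reader might infer that the control arm goes unobserved. The calls and visits are for all patients, the hypoglycaemia outcome has no arm restriction, and SMBG patients test four times a day with a weekly 7-point profile.
- A reader might infer that severe hypoglycaemia outside the wear phase will go uncounted. The documents leave its window and method unspecified; counting is not assured, but it is not excluded.
- A reader might take the weeks without stated calls as the proportion of events lost. Serious events can be recalled at a later visit, so contact time does not measure ascertainment.
- A reader might infer that there is no contact outside the wear phases. Training and the month-3 and month-6 HbA1c measurements imply some, and the flow chart may list more.

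It is also fair to say that 0.4 to 0.6 expected cases per device arm cannot support a comparison of devices, however well they are collected.

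None of this supplies a DKA outcome, a severity definition or a collection method. The general good-practice commitment under Ethical Justification does not supply them either, and further visits would not add an outcome that the list omits.

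**Conclusion.** The point holds in limited form. DKA is not an outcome in any arm or period. Severe hypoglycaemia is not separated from other hypoglycaemic events. Apart from the undefined hypoglycaemia count, the only harm item depends on device attribution and has no SMBG counterpart. Event collection is not described outside a stated contact phase that covers about 15% of the primary HbA1c period.

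The likely number of severe hypoglycaemia cases is small, about 2 in 80 over 26 weeks. That figure assumes the two cited trials' rates carry over to this population, that risk is constant in time, and that nobody drops out. The loss is therefore of a complete descriptive account beside the HbA1c result, not of a testable contrast. The conclusion rests on the visible text; the flow chart could show extra visits. The change should be made because it is cheap and the data are hard to recover later.

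**What to change.** Replace the device-complication line with:

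> Severe hypoglycaemia (needing another person's help), DKA and any diabetes-related admission, in all three arms, from randomisation to month 6, whatever the cause; plus device-related complications in the CGM arms.

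Keep the existing hypoglycaemia count as a separate item. Record the new set on one short structured form, with the same questions in every arm, at contacts that already exist: training, the weekly wear-phase visits, and the month-3 and month-6 HbA1c visits. Tabulate patients with at least one event by arm and period, beside HbA1c, without a formal test.

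Cost: one form page and one table. Recall over about 11 weeks may miss some events, which is why the set is limited to serious, memorable ones.

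Separately, state whether the daily calls and weekly visits also apply after crossover. If they are not already planned, adding them is not free: 14 × 80 = 1,120 calls and 2 × 80 = 160 visits if all patients are covered. The form does not depend on that decision.

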assigned to 26 weeks of unmasked rtCGM (Dexcom G5 Mobile system) or to the control group (continuing with SMBG). Block randomisation with 1:1 allocation was done centrally and control participants wore a masked rtCGM system during the follow-up phase (weeks 22-26). The primary outcome was the baseline-adjusted number of hypoglycaemic events (defined as glucose ≤ 3.0 mmol/L for ≥ 20 min) during the follow-up phase. In the study, 149 participants were randomly assigned (n=74 to the control group; n=75 to the rtCGM group) and 141 completed the follow-up phase (n=66 in the control group, n=75 in the rtCGM group). The mean number of hypoglycaemic events per 28 days among participants in the rtCGM group was reduced from 10.8 (SD 10.0) to 3.5 (4.7); reductions among control participants were negligible (from 14.4 [12.4] to 13.7 [11.6]). Incidence of hypoglycaemic events decreased by 72% for participants in the rtCGM group (incidence rate ratio 0.28 [95% CI 0.20-0.39], $p < 0.0001$), thus CGMS reduced number of hypoglycemic events in T1D (16).

Ólafsdóttir et al performed evaluations from the GOLD randomized trial, an open-label multicenter crossover randomized clinical trial (n = 161) over 69 weeks comparing CGM to SMBG in persons with T1D treated with MSI and they used masked CGM and the hypoglycemia confidence questionnaire for evaluations. It was found that time with nocturnal hypoglycemia, glucose levels < 70 mg/dL was reduced by 48% (10.2 vs. 19.6 min each night, $P < 0.001$) and glucose levels < 54 mg/dL by 65%. (3.1 vs. 8.9 min, $P < 0.001$). For the corresponding glucose cutoffs, daytime hypoglycemia was reduced by 40% (29 vs. 49 min, $P < 0.001$) and 54% (8 vs. 18 min., $P < 0.001$), respectively. Compared with SMBG, CGM use improved hypoglycemia-related confidence in social situations ($P = 0.016$) and confidence in more broadly avoiding serious problems due to hypoglycemia ($P = 0.0020$). Persons also reported greater confidence in detecting and responding to decreasing blood glucose levels (thereby avoiding hypoglycemia)

during CGM use ($P = 0.0033$) and indicated greater conviction that they could more freely live their lives despite the risk of hypoglycemia ($P = 0.022$). Hence, CGM reduced time in both nocturnal and daytime hypoglycemia in persons with T1D treated with MSI and improved hypoglycemia-related confidence, especially in social situations, thus contributing to greater well-being and quality of life(28).

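### No analysis is fixed for any continuous outcome, HbA1c included: an under-specified normality pre-test decides, and its three-group fallback is a two-group test

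*Combined protocol and SAP*

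**What the plan says.** The Statistical Analysis section opens with "Statistical analysis will be performed according to the results obtained from parameters". It then refers to "continuous data, assumed to be normally distributed", and shortly afterwards says "The normality of quantitative data will be checked by measures of Kolmogorov-Smirnov tests of normality". The choice of test follows: "ANOVA or Mann Whitney U test will be applied to compare 3 groups at a time depending upon the normality of the data". The level is common to everything: "All the statistical tests will be two-sided and will be performed at a significance level of" 0.05.

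No outcome has its own named analysis. The primary objective is the reduction in HbA1c at 3 months, rt-CGM against is-CGM. Under Methodology the arms are set out as "With a 1:1:2 randomization ratio in 3 arms with sample size of 20:20:40 participants", and randomisation is balanced over two HbA1c bands (8-10% and 10-12%). The sample size is expressed as a difference on the HbA1c scale: "Sample size of 17 is requires for a power of 80% to detect 0.5% change in HbA1c between both groups".

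**The concern.** There are two separate faults.

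First, the effect measure is not known until the outcome data have been tested. ANOVA compares means; a rank test compares distributions by rank. These are different questions, and only the first matches the 0.5% HbA1c difference behind the sample size. The pre-test also lacks three specifications: the unit it is applied to, whether its critical value is corrected for an estimated mean and SD, and a rule for arms that disagree. In an open-label trial, this leaves the analyst room to choose after seeing the data.

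Second, Mann-Whitney U cannot compare three groups at once, so the fallback has to be replaced or split into pairwise tests when the time comes.

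Neither branch uses baseline HbA1c or the stratum on which randomisation is balanced.

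**Working it through.** **Inputs.** Arm sizes of 20, 20 and 40 come from the protocol. (17/0.9 = 18.9, so 19 after 10% attrition, close to the 20 stated.) The plan gives no operating figure for the pre-test, so there is none to reproduce. Shapes are assumptions, matched to figures in the Review of literature:
- Hypoglycaemic event counts per 28 days in the rt-CGM trial in impaired awareness or prior severe hypoglycaemia: mean 10.8, SD 10.0 at baseline; 3.5, SD 4.7 on rt-CGM; 13.7, SD 11.6 in controls at follow-up (negative binomial).
- Minutes per day below 70 mg/dL in the 24-week CGM trial in adults on multiple injections: median 43, IQR 27-69 (log-normal, sigma = ln(69/27)/1.349 = 0.70).
- Percent time below 70 mg/dL in the normal-awareness trial, home phase, reading the garbled text as 5.3 ± 2.5 and 7.3 ± 4.4 (gamma).

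**Step 1: rejection rate in one arm.** Let p20 and p40 be the simulated probabilities that a corrected Kolmogorov-Smirnov test at 0.05 rejects normality at n = 20 and n = 40.

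**Step 2: three arms together.** With independent arms:
- conflicting verdicts = 1 − p20²·p40 − (1 − p20)²·(1 − p40)
- at least one arm rejects = 1 − (1 − p20)²·(1 − p40)

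| Assumed shape | p20 | p40 | Conflict | Any arm rejects |
|---|---|---|---|---|
| Exactly normal | 0.05 | 0.05 | 14% | 14% |
| Counts 10.8 / 10.0 | 0.50 | 0.847 | 75% | 96% |
| Minutes below range 43 (27-69) | 0.54 | 0.85 | 72% | 97% |
| Counts 13.7 / 11.6 | 0.427 | 0.76 | 78% | 92% |
| Counts 3.5 / 4.7 | 0.883 | 0.999 | 22% | >99% |
| Percent time 5.3 ± 2.5 | 0.172 | 0.297 | 51% | 52% |
| Percent time 7.3 ± 4.4 | 0.248 | 0.456 | 66% | 69% |

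Worked line (10.8 / 10.0): 1 − 0.25 × 0.847 − 0.25 × 0.153 = 0.75. Direct simulation of the three arms agrees to within about a percentage point in every row.

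**Step 3: the unstated choices matter.** For the counts with mean 10.8, the same rule leads to the rank test in about 50% of trials (one arm of 20, corrected), 96% (any arm, corrected), over 99% (pooled n = 80, corrected) or 1-2% (one arm of 20, uncorrected). For minutes below range, the uncorrected rate at n = 20 is about 4-6%.

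**Step 4: HbA1c.** With an assumed uniform 8-12% baseline plus noise, one arm of 20 is flagged in 5-6% of samples (corrected), about the nominal rate, and a pooled 80 in 10%. Under an any-arm rule the figure is 15-21%, against 1 − 0.95³ = 14% for exactly normal data.

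**Step 5: error rates of the pre-test rule.** These used 20/20/40, a corrected test, an any-arm trigger and Kruskal-Wallis as the fallback. Type I error was 4.5-5.8%, against 4.2-5.6% for ANOVA and 4.5-5.3% for Kruskal-Wallis when fixed in advance. With one arm scaled by 0.6 (assumed), power for ANOVA / Kruskal-Wallis / pre-test rule was:
- 88 / 93 / 93% (log-normal, sigma 0.5)
- 41 / 60 / 60% (sigma 0.75)
- 17 / 37 / 37% (sigma 1.0)
- 58 / 60 / 61% (gamma, shape 2)

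**Step 6: the fallback as pairwise tests.** Three unadjusted Mann-Whitney tests at 0.05 on 20/20/40 gave a family-wise error of 11.6% and, in a rerun, 11.9%. The value for independent tests would be 14.3%; sharing arms lowers it.

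**The case against.** The strongest reply is that the pre-test does little inferential damage. Type I error stays near 5%, and its power matched or came close to the better test in the cases simulated. That stands, provided a valid three-group rank test replaces Mann-Whitney U.

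Some stronger readings are tempting, and the documents do not support them:
- A reader might infer that skewed outcomes go to ANOVA or a rank test almost by chance. That describes one arm of 20 with moderate skew and a corrected test. At n = 40, pooled, or with an any-arm trigger, the two skewed outcomes flagged about half the time at n = 20 go to the rank test in 84% of trials or more. With an uncorrected test in an arm of 20, they go to ANOVA nearly always.
- A reader might infer that hypoglycaemia counts will often be analysed as normal. That needs the uncorrected version or a single-arm check, and the plan specifies neither. The on-treatment counts (3.5, SD 4.7) are flagged in 88% of samples even at n = 20.
- A reader might infer that the 8-12% entry range makes HbA1c fail the test. It adds little beyond the nominal rate, it limits entry values only, and no HbA1c distribution or SD is given.
- A reader might take 12% as the trial's false-positive rate. The plan never says that it will run three unadjusted tests, and for the single rt-CGM against is-CGM contrast a two-group test is valid.

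The quoted counts also come from patients with impaired awareness or prior severe hypoglycaemia, whereas this trial excludes a Gold score of 4 or more. They illustrate shape only. The normal-awareness figures imply milder skew and 51-66% conflict.

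Finally, the plan's means or medians would still be in HbA1c units. What is missing is a between-group estimate with a confidence interval.

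**Conclusion.** The point holds on the wording of the plan alone. No analysis is fixed for any continuous outcome, the deciding pre-test lacks a unit, a correction and a tie-break, and the three-group fallback is a two-group test. The size depends on assumed shapes. Conflicting arm verdicts occur in about 70-75% of trials for the two main illustrations, and in 22-78% over all the quoted figures. The 12% family-wise error depends on an assumed pairwise use of Mann-Whitney U.

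The consequence is a reported effect (mean or rank) that depends on the data, and lost precision. Baseline HbA1c goes unused, and ANOVA loses power if it ends up applied to heavily skewed data (41% against 60% at sigma 0.75). It is not an excess of false positives. The gain from baseline adjustment cannot be sized, because the documents give neither an SD nor a baseline-to-follow-up correlation. This should be changed before analysis, but it does not by itself invalidate the trial.

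**What to change.** Delete the normality pre-test and name one analysis per outcome in advance:
- **HbA1c at 3 months (primary, rt-CGM against is-CGM):** linear model with treatment, baseline HbA1c and HbA1c stratum (8-10%, 10-12%), reporting the mean difference and 95% CI. A two-period within-patient mixed model with a period term is supportive only, so the 3-month target does not change.
- **Hypoglycaemic event counts:** negative binomial regression with observation time as offset, reporting a rate ratio and 95% CI.
- **Other continuous outcomes:** the same linear model, with the baseline value where it is collected.
- **Any three-group rank test:** Kruskal-Wallis, as a sensitivity analysis only.

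Remove the opening sentence that lets the analysis follow the results. The cost is SAP wording and slightly more analyst time than ANOVA. No data collection changes.
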